**Investigation of the Effectiveness of Visual Feedback
Training on Upper Extremity Functions in Cerebral Palsy**

**Study Protocol with Statistical Analysis Plan (SAP) and
Informed Consent Form (ICF)**

January 1, 2018

**Investigation of the Effectiveness of Visual Feedback
Training on Upper Extremity Functions in Cerebral Palsy**

Study Protocol

(Pages 2 – 6)

January 1, 2018

Study Protocol

Study titled 'Investigation of the Effectiveness of Visual Feedback Training on Upper Extremity Functions in Cerebral Palsy was approved by Marmara University Faculty of Medicine Clinical Researches Ethics Committee meeting on 05.01.2018 with approval number: 09.2018.007 (Annex-1).

The legal representatives of the children who participated in the study were informed about the aim, duration and the programs to be applied throughout the study. Volunteer Information Form has been signed and approved in accordance with the standards deemed appropriate by the Clinical Researches Ethics Committee of Marmara University Faculty of Medicine (This form can be seen on Informed Consent Form (ICF) section). The study was conducted in accordance with the Declaration of Helsinki.

Hypothesis of the Study

H0: Addition of the exercises performed with Cogniboard® Light Trainer device to the neurodevelopmental (NDT) based rehabilitation program in patients with cerebral palsy does not contribute positively in improving the efficiency of upper extremity functions.

H1: Addition of the exercises performed with Cogniboard® Light Trainer device to the neurodevelopmental (NDT) based rehabilitation program in patients with cerebral palsy contributes positively to improve the efficiency of upper extremity functions.

Randomization of the Study Groups

Children with Cerebral Palsy who applied to the Dilbade Education and Rehabilitation Center for rehabilitation were invited to participate to the study. Children who volunteered to participate and whom met the criteria for participation were randomized with simple random sampling method and divided into two groups. Individual Neurodevelopmental (NDT) based rehabilitation programs were applied to the participants in both groups. The Cogniboard® Light Trainer education system was added to the rehabilitation program of the Group II (the study group).

Inclusion Criteria

- Volunteered to participate,
- The child and the family have agreed to participate in the study,
- Having a diagnosis of Cerebral Palsy,
- Children aged between 4 - 18 years,
- Having upper extremity spasticity (0), (1), (1+) according to the modified Ashworth Scale (MAS)
- To be able to cooperate to the exercises

Exclusion Criteria

- Botulinum Toxin (BOTOX) injection applied to the upper extremity within the last 6 months,
- Congenital deformity in upper extremity
- Epileptic attack history,
- Any cardiac or orthopedic problem,
- Visual or hearing impairment

Applied Evaluations

Evaluations are applied twice: before and after the study. All evaluation data are noted to 'Participants Tracking Form' (Annex-2). Spasticity was defined with 'Modified Ashworth Scale'; upper extremity joint range of motion (ROM) with 'goniometer'; grip and pinch strength with 'dynamometer'; hand skills with 'Minnesota Hand Skill Test'; functional abilities with 'Childhood Health Assessment Questionnaire (CHAQ)' and functional level with 'Gross Motor Function Classification System (GMFCS)'

Treatment Program

The participants in our study were all rehabilitated in Dilbade Education and Rehabilitation Center twice a week for 8 weeks, a total of 16 sessions (Duration of one session is 45 minutes).

Group I (Control Group) received individual Neurodevelopmental (NDT) based rehabilitation program.

Group II (Study Group) received individual NDT based rehabilitation program (35 minutes) + Cogniboard® Light Trainer education (10 minutes).

Cogniboard® Light Trainer Education Protocol

Upper limb exercises were applied to the study group with the device which is a training program with visual feedback for 10 minutes in addition to individual 35 minutes neurodevelopmental treatment program. Devices were placed in the mirror so that the participants could see their own reflection. The distances of the participants to the mirror were proportional to their height. For children between 100-149 cm, the distance of the child with the mirror was set as 40 cm and for the children between 149-175 cm, 50 cm. Eight devices were placed in the mirror within the reach of the participant. While the shoulder and wrist were flexed, the shoulder was placed in the lateral distances that the shoulder could reach while the shoulder was in 90°, while the shoulder was in extension and the other devices were placed between these points (Picture 1).

(Picture 1. Application of Cogniboard® Light Trainer Education Device)

Neurodevelopmental Therapy (NDT) Based Upper Extremity Rehabilitation

In accordance with the needs of the patients for their gross motor functions, the children in both groups were included in the NDT program, which was determined according to the age, sex, mental status and preferences of the individual. NDT program included; rehabilitation of muscle tonus disorders, sensory-perception-motor integrity enhancement, exercises to increase upper extremity functions, stretching and strengthening exercises due to muscular shortness and weakness, exercises to accommodate movements in daily life, and training of activities such as standing up, eating, walking, body care.

**Investigation of the Effectiveness of Visual Feedback
Training on Upper Extremity Functions in Cerebral Palsy**

Statistical Analysis Plan (SAP)

(Pages 7 – 8)

January 1, 2018

Statistical Analysis Plan (SAP)

The statistical program Statistical Package for Social Sciences (SPSS) Version 11.5 (SPSS Inc., Chicago, IL, USA) was used in the data analysis of the study. The p value of $p<0.05$ was considered to be statistically significant in the data analysis. Shapiro-Wilks test was used to investigate the appropriateness of the variables to normal distribution.

In the comparison of the nominal characteristics of the participants in both groups, such as gender, CP type, GMFCS and dominant side, Fisher Precise Chi-Square Test was used.

The initial demographic characteristics such as age, height, weight, body mass index (BMI) of the participants in both groups and the changes before and after the treatment were compared with Independent Samples t-Test and Paired Samples t-Test.

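### Age is neither balanced at allocation nor adjusted for in the analysis, so in a small trial of 4 to 18 year olds a chance age imbalance would go uncorrected and precision is lost

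*Combined protocol and SAP*

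**What the plan says.** - **Allocation** (protocol, Randomization of the Study Groups): eligible volunteers "were randomized with simple random sampling method and divided into two groups". No ratio, block, stratum or minimisation factor is described.
- **Population and setting** (Inclusion Criteria; Treatment Program): "Children aged between 4 - 18 years", all treated at one centre.
- **Therapy content** (section on NDT-based upper extremity rehabilitation): both groups receive an individual NDT programme, "which was determined according to the age, sex, mental status and preferences of the individual".
- **Baseline comparison** (SAP): t-tests are planned for "The initial demographic characteristics such as age, height, weight, body mass index (BMI) of the participants in both groups". For sex, CP type, GMFCS and dominant side the SAP uses a Fisher test.
- **Outcome comparison** (SAP, in the same sentence as the baseline t-tests): "the changes before and after the treatment were compared with Independent Samples t-Test and Paired Samples t-Test".
- No covariate is named anywhere in the SAP, and nothing is said to follow if a baseline comparison shows a difference.
- **Data held** (Annex 2, tracking form): age, date of birth, and the before- and after-treatment values of range of motion, strength and hand-skill times.

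**The concern.** Ages 4 to 18 cover a wide span of development. A plan can deal with a strong prognostic factor at allocation, by restricting the randomisation, or at analysis, by putting the factor in the model. As described, this plan does neither. Its only use of age is a significance test at baseline. That test cannot correct an imbalance: under proper randomisation any difference is due to chance, and the test leads to no action.

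The plan itself gives a reason to think age could bear on response, because the NDT content depends on the child's age. That content is the whole of the control programme and 35 of the 45 minutes in the study group. Two groups of different mean age may therefore also receive somewhat different therapy.

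Two things are at stake. If one group happens to be clearly older, a positive or null result could be put down to age and the planned analysis could not answer. And in every trial, balanced or not, variation in change that age explains stays in the error term.

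**Working it through.** **Inputs.** From the documents: ages 4 to 18, alpha 0.05, t-tests without covariates. The documents give no sample size, age distribution, SD or correlation, so these are assumed: total N of 20, 30 or 40; uniform ages; two-sided testing; a correlation r between age and change of 0, 0.3 or 0.5. The plan states no figure to reproduce.

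**Step 1: how often a 2-year age gap arises.** For uniform ages, SD = (18 − 4)/√12 = 4.04 years. With equal groups, the standard error of the difference in mean age is 4.04 × √(4/N), and the chance of a gap of at least 2 years is 2 × [1 − Φ(2/SE)]. With coin-toss allocation, group sizes vary and the chance is slightly higher; that column is simulated, with 20,000 allocations per N.

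| N | SE (years) | Equal groups | Coin toss |
|---|---|---|---|
| 20 | 1.81 | 26.8% | 28.7% |
| 30 | 1.48 | 17.5% | 18.3% |
| 40 | 1.28 | 11.8% | 12.2% |

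The range is about 12% to 29%, and it hardly depends on which of the two procedures was used.

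**Step 2: what such a gap does to the result.** The SAP compares changes, so age matters through its slope on change. A 2-year gap shifts the difference in mean change by r × 2/4.04 SD:

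- r = 0: no shift
- r = 0.3: 0.3 × 0.495 = 0.15 SD
- r = 0.5: 0.5 × 0.495 = 0.25 SD

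**Step 3: false positives.** Null simulation, 8,000 trials per setting, comparing the t-test on change with a linear model of change on group and age. The last two columns take only trials in which mean ages differ by at least 0.5 SD (0.5 × 4.04 = 2.02 years).

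| N | r | t-test, all trials | t-test, imbalanced | Age-adjusted, imbalanced |
|---|---|---|---|---|
| 20 | 0.3 | 5.5% | 6.9% | 4.5% |
| 30 | 0 | 5.0% | 5.1% | 5.6% |
| 30 | 0.3 | 5.1% | 8.0% | 5.7% |
| 30 | 0.5 | 5.4% | 11.4% | 4.3% |
| 40 | 0.3 | 4.9% | 7.6% | 5.3% |

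Over all trials the unadjusted test is sound. The excess appears only in imbalanced trials, and only when age predicts change. The imbalanced columns rest on a fraction of the runs, so differences of about one percentage point there are noise.

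**Step 4: precision.** Adjusting for age multiplies the residual variance of change by 1 − r²: 1.00, 0.91 and 0.75 at r = 0, 0.3 and 0.5. For an assumed standardised effect of 0.8, the total sample for the usual 80% power falls from 50 to 46 at r = 0.3 and to 38 at r = 0.5. Adding the before-treatment score brings a further gain that depends on its correlation with the after-treatment score, which the documents do not give.

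**The case against.** The strongest reply is that the plan compares changes. Grip strength or placement time may depend heavily on age, but a constant difference in level cancels when the before value is subtracted. Age then matters only if it predicts 8-week change, and the documents give no figure for that. This stands. It is why the shift runs from 0 upward, and why the age-dependence of the NDT content is a reason for caution and not evidence of bias. Nor do the CHAQ instructions show age-dependence: the Not Applicable response is there to keep normal age limits out of the answers.

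Four stronger readings are tempting, and the documents do not support them.

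- **Any age imbalance carries straight into the result.** It does not, for the reason just given.
- **The test is invalid.** Randomisation keeps the overall type I error near 5%. The fault is conditional on the imbalance that occurs.
- **Allocation was by coin toss, so group sizes were left to chance.** The wording could equally mean drawing a fixed number of children into one group. Even if sizes did vary, unequal groups do not bias a t-test. At an assumed effect of 0.8, a 60:40 split costs about 2 power points (59% to 57% at N = 30; 72% to 70% at N = 40).
- **The t-test was run on raw after-treatment scores.** That would be more exposed to age, but the SAP sentence refers to changes.

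It might also be said that the real remedy is a blocked, age-stratified list. The protocol reports randomisation in the past tense, so this may come too late. It is also a trade-off: the light training is visible and there is one centre. With blocks of 2 and 4 in equal mix, someone tracking allocations could guess about 72% correctly, against 50% under simple randomisation. Leaving allocation unrestricted is defensible, provided the analysis adjusts.

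**Conclusion.** The point holds in a limited form. Age is not balanced by any described feature of the allocation and is not used in the outcome analysis, so a chance imbalance would go uncorrected and precision is lost. It is a weakness of efficiency and interpretability; it does not invalidate the comparison.

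On the assumptions above, a 2-year gap in mean age arises in about 12% to 29% of allocations and moves the difference in mean change by 0 to 0.25 SD. Among trials with a gap of at least 0.5 SD at these sample sizes, the false-positive rate is about 7% to 8% at r = 0.3 and about 11% at r = 0.5 (N = 30), against roughly 4% to 6% with age in the model. If age does not predict change, there is no distortion and nothing to gain from adjusting for age.

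A larger trial would see such gaps less often: about 5% of allocations at N = 60. Ages bunched more closely than uniform would also make a 2-year gap rarer. The simulated adjustment used age alone; the model proposed below also includes the before-treatment score.

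**What to change.** Keep the allocation as it is. In the SAP:

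1. Replace the between-group independent t-test on change with a linear model (ANCOVA) for each continuous outcome: after-treatment score on group, before-treatment score and age in years. Report the adjusted group difference with its 95% confidence interval.
2. Remove the significance test on baseline age. Show age by group descriptively.
3. Fix the covariates in advance, so that adjustment does not depend on whether an imbalance is seen.

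In the protocol, add one sentence saying how the random allocation was carried out, including whether group sizes were fixed.

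The cost is a few lines of text. Age and the before-treatment scores are already on the tracking form, so no extra children, visits or measurements are needed. The model uses two more degrees of freedom than the t-test (N − 4 against N − 2; 16 against 18 at N = 20). That is a small loss if neither covariate is prognostic, and it is outweighed if either is moderately so.

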Annex 2. Participants Tracking Form

Participant's Name - Surname:

Legal Representative Name - Surname:

Phone number:

Age / Gender:

Height:

Weight:

Date of birth:

Type of Cerebral Palsy (CP) (Mark X): **Spastic** **Diskinetic** **Ataxic**

Which side of the arm is effected mostly?

Which side is your dominant side?

How did the problem occur? (Preterm birth, after birth etc. Please explain.)

How many years have you been going to a rehabilitation center?

Did you have any operations? Please write if you did:

Are you using any device? If so, what are they?

Evaluations:

Muscle Tone: (According to the Modified Ashworth Scale 0/1/1+/2/3/4)

Right or Left Arm (Please mark)

Hand Wrist Function:

Elbow Flexion:

Supination:

Do you have any additional medical problems?

Yes / What is it?:

No:

[figure not shown]
Range of Motion:		Before Treatment	After Treatment
Shoulder	Flexion		
	Abduction		
Elbow	Flexion		
Front Arm	Extension		
	Supination		
	Pronation		
Hand Wrist	Flexion		
	Extension		

Muscle Strength	Before Treatment	After Treatment
Grasping		
Tip Pinch		
Lateral Pinch		
Triple Pinch		

Minnesota Hand Skill Test	Before Treatment	After Treatment
Placement with the affected hand (sn)		
Placement bilaterally (sn)		

Gross Motor Functional Classification System (GMFCS)

Level of the participant:

1

CHILDHOOD HEALTH ASSESSMENT QUESTIONNAIRE

2

In this section we are interested in learning how your child's illness affects his/her ability to function in daily life. Please feel free to add any comments on the back of this page. In the following questions, please check the one response which best describes your child's usual activities (averaged over an entire day) **OVER THE PAST WEEK, ONLY NOTE THOSE DIFFICULTIES OR LIMITATIONS WHICH ARE DUE TO ILLNESS**. If most children at your child's age are not expected to do a certain activity, please mark it as "Not Applicable". For example, if your child has difficulty in doing a certain activity or is unable to do it because he/she is too young but not because he/she is RESTRICTED BY ILLNESS, please mark it as "NOT Applicable".

3

	Without ANY Difficulty	With SOME Difficulty	With MUCH Difficulty	UNABLE To do	Not Applicable
--	------------------------------	----------------------------	----------------------------	-----------------	-------------------

4

DRESSING & GROOMING

5 Is your child able to:

6 - Dress, including tying shoelaces and doing buttons?

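### Annex 2 prints the baseline reading beside the after-treatment entry for 14 assessor-dependent measurements, and the available text describes no masking of the assessor

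*Combined protocol and SAP*

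**What the plan says.** Under Applied Evaluations the protocol sets two assessment times: "Evaluations are applied twice: before and after the study". Both go to one place: "All evaluation data are noted to 'Participants Tracking Form' (Annex-2"). The same section names the instruments, among them "upper extremity joint range of motion (ROM) with 'goniometer'; grip and pinch strength with 'dynamometer", together with the Minnesota test of hand skill.

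Annex 2 is a single form that opens with "Participant's Name - Surname". Its strength table is headed "Muscle Strength Before Treatment After Treatment" and its hand-skill table "Minnesota Hand Skill Test Before Treatment After Treatment"; the range-of-motion table has the same two columns. The Minnesota rows, such as "Placement with the affected hand (sn"), are timings. The form has no field for the study group.

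On the groups, Randomization of the Study Groups says: "The Cogniboard® Light Trainer education system was added to the rehabilitation program of the Group II (the study group"). Under Treatment Program all children attend one centre, only Group II uses the device, and no sham is described. The SAP compares the before-after changes with independent-samples and paired t-tests and takes p<0.05 as significant.

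**The concern.** Goniometer alignment, encouragement during a grip or pinch effort, and starting and stopping a timed task all depend in part on the person measuring. If that person can see the first value while taking the second, the two readings are no longer independent measurements, and the difference between them is what the SAP analyses.

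Two effects need to be kept apart. Sight of the baseline can move the after reading in either direction: toward the earlier value, or toward an expected gain. This affects the before-after changes in both groups and the paired tests built on them. Knowledge of the group is what can make the movement differ between arms, and so bias the comparison that bears on H1. Randomisation does not protect against a difference that enters at measurement, and neither does the choice of test. With one centre and visibly different sessions, staff could easily know a child's group.

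**Working it through.** **Step 1. Which measurements the layout affects (Annex 2).**

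- Range of motion: shoulder 2, elbow 1, forearm 3, wrist 2, total 8 rows with before and after columns.
- Strength: grasp and three pinches, total 4 rows.
- Minnesota: affected hand and bilateral, total 2 rows.
- Sum: 8 + 4 + 2 = 14.
- Modified Ashworth and gross motor classification each have a single entry, and the childhood health questionnaire has no before and after columns. The layout point does not cover these three.

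**Step 2. What the text says about the assessor.** The available text mentions no masking, no independent assessor, no separate sheet for the second visit, and not who takes the readings. Part of the document was not available, so this is a statement about the text at hand only.

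**Step 3. Direction.** Let s be the shift that the assessor adds to the after reading.

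- Same s in both arms: (device change + s) − (control change + s) = device change − control change. The between-group comparison is unchanged, but each paired test is off by s.
- Shift b in the device arm only: the between-group difference is off by b. This requires that the assessor knows, or correctly guesses, the group.

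**Step 4. Illustration of size.** The documents give no sample size, SD or effect size, so there is no figure of the plan to reproduce. Assumptions: n children per arm from 10 to 30; no true effect; b from 0 to 0.5 in units of the SD of the change; independent-samples t-test, two-sided 0.05 (the SAP does not state sidedness).

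The test statistic follows a noncentral t with df = 2n − 2 and noncentrality b × √(n/2). The chance of a false significant result favouring the device is P(T > t at 0.975).

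Example, n = 15 and b = 0.3: df = 28, critical value 2.048, noncentrality 0.3 × √7.5 = 0.82, probability 12.2%.

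| n per arm | b = 0 | 0.1 | 0.2 | 0.3 | 0.5 |
|---|---|---|---|---|---|
| 10 | 2.5% | 4.0% | 6.2% | 9.3% | 18.4% |
| 15 | 2.5% | 4.5% | 7.6% | 12.2% | 26.2% |
| 20 | 2.5% | 4.9% | 9.0% | 15.0% | 33.8% |
| 30 | 2.5% | 5.7% | 11.5% | 20.7% | 47.8% |

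The table shows what a group-dependent shift would do if present. It is not evidence that one is present.

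**The case against.** The strongest reply is that the form is not what would favour the device. Columns visible in both arms have no direction between arms, anchoring on the baseline could just as well pull readings toward no change, and the form carries no group label. This stands. A reader might infer from the layout that assessors work with the baseline in view and the group known. No section says so: the protocol names the form on which data are recorded, which does not exclude copying from another sheet, and it is silent on the assessor. The supportable statement is that nothing in the available text prevents either.

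It also stands that separate sheets alone would leave an assessor who knows the group free to encourage or align differently, and that a code in place of a name hides nothing from someone facing the child. The number of therapists at the centre is not given, so a non-treating assessor cannot be assumed to be available; colleagues at a single centre may know the group anyway. The illustrative range, from 4.0% to 47.8% over the assumed non-zero shifts, is too wide to rank the problem by size. Finally, much of the protocol is in the past tense, so a change of procedure may come too late.

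None of this removes the core point. The protocol directs both sets of readings to a form that, as printed, puts the first value next to the space for the second, and it describes no safeguard.

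**Conclusion.** The concern holds in limited form. For 14 assessor-dependent measurements, Annex 2 used as printed makes the baseline value available at the repeat reading, and the available text neither describes masking nor identifies the assessor. This can distort the before-after changes and the paired t-tests. Bias toward the device arises only if the assessor also knows the group; the visible baseline then makes such a bias easier to act on.

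Two stronger readings are not supported: that the layout by itself favours the device, and that the assessors were in fact unmasked. The size is unknown. The percentages rest entirely on assumed sample sizes and shifts. The point deserves action because the safeguard is cheap, not because a bias of a given size has been shown.

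**What to change.** 1. Split Annex 2 into a baseline sheet and a separate post-treatment sheet that carries a participant code and no name. Collect the baseline sheet before treatment starts and withhold it from the person taking the after readings. The cost is reprinting one form as two and a little form handling. This removes the visible baseline; it reduces the risk of bias toward the device but does not remove it.

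2. Where existing staffing allows, and with no added staff, have the after readings, including any repeat Modified Ashworth rating, taken by a therapist who did not treat that child and is not told the group. Ask the family not to mention it. The cost is some scheduling, and a child or parent may still reveal the group.

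3. In either case, state in the protocol who takes the readings and whether that person is masked to group and to baseline values.

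4. If the readings have already been taken, state who assessed, whether they knew the group and whether they saw the baseline values, and report any lack of masking as a limitation. This costs a few sentences.

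### In the text available for review, H1 has no primary outcome, no multiplicity rule and no stated deciding test, so the chance of a false claim for the device is not controlled

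*Combined protocol and SAP*

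**What the plan says.** - **Hypothesis of the Study.** H0 is that the added exercises "does not contribute positively in improving the efficiency of upper extremity functions"; H1 is that the addition "contributes positively to improve the efficiency of upper extremity functions". Neither names an instrument or a variable.
- **Applied Evaluations.** Six evaluations are listed without ranking: Modified Ashworth Scale (MAS), range of motion, grip and pinch strength, Minnesota test, CHAQ and GMFCS. The section adds: "Evaluations are applied twice: before and after the study".
- **Statistical Analysis Plan.** A p value below 0.05 "was considered to be statistically significant in the data analysis". The available text does not say one- or two-sided, and mentions no adjustment. The sentence on baseline characteristics also says that "the changes before and after the treatment were compared with Independent Samples t-Test and Paired Samples t-Test". It does not list the outcomes or say which of the two tests answers H1.
- **Annex 2.** The tracking form has before and after columns for 8 range-of-motion rows, 4 strength rows and 2 Minnesota times, 14 in all. MAS and GMFCS have single entries, and the CHAQ form is appended without such columns.

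One part of the combined document, between the SAP's t-test sentence and Annex 2, was not available. Nothing here is a statement about its content.

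**The concern.** A formal H0/H1 pair with a significance threshold is a confirmatory claim, and its error rate depends on which result, from which test, counts as support. Here many results could be offered and none is designated. Whichever falls below 0.05 in the device's favour could become the headline, and nothing in the available text rules that out.

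The choice of test matters separately. An independent t-test on change compares the arms. A paired t-test asks only whether one arm changed from its own baseline. Both arms receive NDT-based rehabilitation, so both may improve. A paired result that is significant in the device arm but not in control is not a comparison of the arms and cannot support H1, yet the SAP sentence leaves room to use it that way.

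**Working it through.** The available text gives no sample size, power or family-wise error rate, so there is no plan figure to reproduce. The check asks how far the chance of a false claim depends on the unstated rule.

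**Inputs from the documents:** the 0.05 threshold (SAP); a directional H1 (Hypothesis of the Study); 8 + 4 + 2 = 14 before/after outcomes (Annex 2).

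**Assumptions:** no true effect on any outcome; between-arm tests; 0.05 is two-sided, so each test has a 0.025 chance of a significant result favouring the device; equal correlation ρ between test statistics, from 0 to 0.9. The documents give no correlation.

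**Formulas.** At ρ = 0 the number of favourable significant results among m outcomes is binomial (m, 0.025):

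- any one of 14: 1 − 0.975^14 = 29.8%
- at least two of 14: 1 − 0.975^14 − 14 × 0.025 × 0.975^13 = 4.7%
- at least three of 14: the previous figure less 91 × 0.025² × 0.975^12 = 0.5%
- any one of three: 1 − 0.975^3 = 7.3%

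For ρ > 0, given a shared standard normal factor x, each test favours the device with probability 1 − Φ((1.96 − √ρ·x)/√(1 − ρ)). The binomial probability is then averaged over x by numerical integration.

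| Rule for supporting H1 | ρ=0 | 0.3 | 0.5 | 0.7 | 0.8 | 0.9 |
|---|---|---|---|---|---|---|
| One named outcome | 2.5% | 2.5% | 2.5% | 2.5% | 2.5% | 2.5% |
| Any one of 14 | 29.8% | 22.4% | 17.4% | 12.4% | 9.9% | 7.0% |
| Any one of three (two Minnesota times, CHAQ) | 7.3% | 6.8% | 6.3% | 5.5% | 4.9% | 4.2% |
| At least two of 14 | 4.7% | 7.5% | 7.6% | 6.8% | 6.0% | 5.0% |
| At least three of 14 | 0.5% | 2.9% | 4.1% | 4.5% | 4.4% | 4.0% |
| At least seven of 14 | 0.0% | 0.1% | 0.5% | 1.3% | 1.7% | 2.2% |

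**Checks.** Simulated two-sample t-tests with an assumed 10, 15 or 20 children per arm gave, for any one of 14, 29.5–30.2% at ρ = 0, 18.0–18.2% at 0.5 and 7.3–7.5% at 0.9, so the normal approximation is adequate. If 0.05 were meant one-sided, any one of 14 would give 51% (ρ = 0) down to 13% (ρ = 0.9), against 5% for one test.

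**Cost of adjustment.** An outcome with 80% power at two-sided 0.05 has an expected statistic of 1.960 + 0.842 = 2.802. Holm's first step over 14 outcomes uses 0.05/14 = 0.00357, with critical value 2.914. Power there is Φ(2.802 − 2.914) = Φ(−0.112), about 46%.

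**The case against.** The strongest reply is that no document says one significant result out of 14 would prove H1. H1 is a single overall statement, and a sensible investigator might look for a consistent pattern. That stands: requiring at least three of 14 gives about 0.5% to 4.5%, and at least seven 2.2% or less. A reader might infer that the plan carries a 30% false-claim rate. It does not: 30% is one rule at zero correlation. What the reply cannot supply is the rule itself.

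Second, Applied Evaluations uses functional language mainly for the Minnesota test and CHAQ, so H1 may concern only those. That is reasonable, and Annex 2 is a data sheet and not a test list. It reduces the inflation to 4–7% without removing it, and the available text does not state the restriction.

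Two further inferences should be resisted:

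- Counting CHAQ and three MAS sites gives 18 outcomes and up to 37%. MAS has single entries on the form and is an eligibility criterion. Only the general sentence about evaluating twice supports counting it.
- A percentage can be put on the paired route: 33–58% for any of 14, at correlations of 0.8–0.9 and an assumed 20–80% paired power. That rests on a decision rule the documents do not state, and falls to about 27–36% if contradictory results block the claim. The SAP sentence can also be read conventionally, as independent tests between arms and paired tests within arms. The logical objection to the paired route holds without a percentage.

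Finally, the unavailable part may contain SAP text that settles the matter, so one cannot conclude that the full plan lacks a primary outcome. If it names one, the sponsor need only point to it. The hypothesis and evaluations sections, where one would also be expected, are available and silent.

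**Conclusion.** The concern holds for the text available. The only hypothesis has no designated outcome, multiplicity rule or deciding test, so the chance of a false claim for the device is not controlled. Its size cannot be fixed from the documents. Under no true effect, two-sided 0.05 and correlations of 0 to 0.9, it runs from about 30% down to 7% if any one of 14 suffices, and from about 7% down to 4% for the three functional outcomes. It is about 5–8% if two of 14 are required and about 0.5–4.5% if three are. A single named test gives 2.5%. That spread is itself the defect: the error rate depends on a rule nobody has written down. This should be corrected before any claim about H1 is made. Confidence is medium, because part of the document could not be checked.

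**What to change.** State in the SAP that:

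1. H1 is decided only by the between-arm comparison of change in one named primary outcome at two-sided 0.05. The sponsor chooses it without reference to the results; Minnesota affected-hand placement time is one candidate.
2. Paired within-arm tests are descriptive and do not support H1.
3. Every other outcome is either Holm-adjusted or reported as exploratory, with a confidence interval and no claim.

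If no outcome data have been seen, this costs wording only. The documents are largely in the past tense. If data have been seen, naming a primary outcome now does not restore the error rate. The choice should then be disclosed as post hoc, every outcome reported, and the adjustment made across all outcomes used to support H1.

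The price is that a raw p just below 0.05 on a non-primary outcome may no longer count as significant. Under Holm over 14 outcomes, an outcome with 80% power at 0.05 keeps about 46% at the first step. A single named primary outcome avoids that loss for the main claim, but only if it is chosen before the results are known.
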